This trial will be conducted in compliance with the protocol, the Data Protection Act and other regulatory requirements as appropriate.

Study Summary:

Study Title	Evaluation of a single use point of care device for the diagnosis of influenza and other respiratory pathogens in clinical upper airway samples using isothermal amplification.
Study Design	A prospective single centre feasibility study carried out in Accident and Emergency department of Imperial College Healthcare NHS Trust in patients presenting with influenza like illness.
Primary Objective	To assess the feasibility of this novel single use product for the diagnosis of influenza and other respiratory pathogens in upper airway samples at the point of care in acute clinical settings and compare the results against the conventional diagnostic methods of Polymerase

	Chain Reaction testing in the laboratory and/or rapid flu testing (Cepheid, Sunnyvale, CA, USA).
Secondary Objectives	
To compare the results obtained in a clinical setting to the analytical study data and laboratory test on stored samples.
 
A further objective is to develop a bank of research samples for further testing of the device in laboratory conditions.

Population	Any consenting adult presenting to the Accident and Emergency department with influenza like illness or a febrile illness associated with symptoms such as cough, sore throat or rhinorrhoea, and for whom a respiratory viral screen is clinically indicated will be recruited.
Eligibility	
Inclusion criteria:
 
 - Any adults ≥ 18 years of age who is: - Able to provide written informed consent, or written informed assent by a relative or carer can be provided - Recruited during initial medical assessment - Able to comply with the study protocol 
Exclusion criteria:
 
 - Previously recruited within 28 days of the current admission - Enrolment in a trial of antimicrobial therapy - If patients are unable to understand verbal or written information in English, hospital translation services will be sought but not guaranteed. However, if the team member seeking consent is not satisfied that the potential recruits' English language ability is sufficient to completely understand the study protocol and requirements (despite use of hospital translation services) then they will not be recruited to the study.

1.1 Background

Influenza is a contagious respiratory illness that is a leading cause of acute respiratory infections and causes a continuous threat to global health, the viruses mutating and spreading in both human and animal populations. In the period from March to May 2009 a novel swine-origin influenza A (H1N1) virus emerged in Mexico and the United States (1,2). Most cases were acute and self-limiting among children and young adults (1) although the global mortality over the first 12 months has been estimated at over 200,000 respiratory deaths (3). Those with severe illness typically presented with viral pneumonitis or pneumonia, sometimes complicated by multi-organ failure.

Although influenza is a clinical diagnosis, diagnostic testing can influence clinical decisions with regards to infection prevention measures by isolation, starting anti-viral treatment and with hospital admissions or hospital discharges.

Current influenza testing can be performed by numerous methods. The gold standard is via molecular assays including rapid molecular assays and reverse transcription polymerase chain reaction (RT-PCR). Serological testing and antigen detection tests including immunofluorescence assays are other methods but the sensitivity and specificity for these tests are variable and tend to be lower than molecular testing methods (4).

In the UK, influenza testing relies on clinical suspicion and the use of respiratory viral PCR in the laboratory (5,6). This can have a turn-around time of 24-48 hours (5), and the public health control of influenza is time critical. With this in mind, point of care (POC) testing has been considered by Public Health England, as platforms with the potential to be used within 20 metres of patients and the results to be available within 10 to 90 minutes for the diagnosis of influenza have been invested in, researched and developed since the late 1990's.

Numerous devices and tests have been developed with the first generation being dependent on viral antigen testing. The second generation devices consisting of nucleic acid amplification technologies (NAAT) (4).

	Sensitivity	Specificity
First generation Single antigen based	50-70%	85-100%
Second generation NAAT based Single target (influenza A+B)	90-99%	95-99%

Second generation NAAT based Multi targets	90-99%	95-99%
--	--------	--------

Table from PHE (4)

The rational for this study is to assess the feasibility of a novel single use product for the diagnosis of influenza and other respiratory pathogen in patients presenting with influenza like illness (ILI).

With the results being available at the POC when patients initially seek medical attention, the aim is to assist with immediate clinical decision regarding the need for isolation due to a respiratory infections, initiation of anti-viral treatment and potential discharge plans. This feasibility study will help develop this POC diagnostic device.

1.2 Hypothesis

The new single use POC device will be feasible to use as a diagnostic device for influenza and other respiratory viruses in a clinical setting.

2. Aims and Objectives

2.1 Primary aims and objectives:

To assess the feasibility of this novel single use product for the diagnosis of influenza and other respiratory pathogen in upper airway samples at the POC in acute clinical settings and compare the results against the conventional diagnostic methods of PCR testing in the laboratory and or rapid flu testing (Cepheid, Sunnyvale, CA, USA).

Usability, performance and final results from the new POC device will be analysed in an acute clinical setting (in a real-life acute setting vs conventional testing). The diagnostic performance of this data will be reviewed and analysed compared to the current standard test of viral PCR results in the laboratory and/or rapid flu testing (Cepheid, Sunnyvale, CA, USA).

2.2 Secondary aims and objectives:

To compare the results obtained in a clinical setting to the analytical study data and laboratory test on stored samples. A further objective is to develop a bank of research samples for further testing of the device in laboratory conditions.

Sensitivity, specificity, positive predictive value and negative predictive value of the new POC device in fresh samples will be calculated and compared to the results on stored samples.

3. Study Design

This is a prospective single centre feasibility study carried out in an acute clinical setting, the Accident and Emergency (A+E) department of Imperial College Healthcare NHS Trust (ICHNT).

The patient will be seen in the clinical setting on a one off visit. Any adult presenting with ILI or a febrile illness associated with symptoms such as cough, sore throat or rhinorrhoea, and for whom a respiratory viral screen is clinically indicated will be recruited if they meet the eligibility criteria.

One nasal swab to be taken per patient recruited in addition to the swab(s) (nasal, nasopharyngeal or throat swab) taken for standard care. Routine sample(s) (A) to be processed for standard PCR testing in the laboratory and/or rapid flu testing (Cepheid, Sunnyvale, CA, USA) as per standard clinical work flow. Second sample (B) to be taken for evaluation under the study and either: (i) transferred to the new device buffer tube and promptly tested in a test device or (ii) if no device is available for prompt testing, add the swab to a viral storage/transport buffer tube as per standard procedures and freeze for long-term storage and later testing.

Tests on this device should be performed 'blinded', i.e. operator unaware of diagnostic standard of care result to ensure clinical decisions/reading of results are not based upon results obtained with prototype tests. The test result should not be disclosed to either the patient or the clinician. Each patient will be expected to participate for a total of 30 minutes.

As this is a feasibility study, diagnostic standard of care tests should be performed as per the clinical pathway with routine sample(s) (A) and the results of the test devices should not affect clinical decisions.

A minimum of 50 devices will be tested with fresh patient samples in a real life clinical setting. Opportunistic patient samples will be collected and banked throughout the study period. The aim will be to recruit as many patients as possible. A target of 200 patients has been set based on 1600 viral PCRs taken at ICHNT last year over the influenza period and a realistic estimate was made for the sample size for patients who may be willing to participate in the study presenting with ILI, with consideration of financial, time and resource constraints. This data will be analysed to review the feasibility for this new device.

The primary outcome will be to review the feasibility and the diagnostic accuracy for viral respiratory pathogens in this novel device using fresh patients' samples in a real-life clinical setting compared to the standard diagnostic testing of a respiratory viral PCR in the laboratory and/or rapid flu swab (Cepheid, Sunnyvale, CA, USA) using sensitivity, specificity, positive predictive value and negative predictive values.

The secondary outcome will be to review the feasibility and the diagnostic accuracy for viral respiratory pathogens in this novel device using fresh patients' samples in a real-life clinical setting compared to the laboratory settings using stored samples using sensitivity, specificity, positive predictive values and negative predictive values.

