5.3 Using single use point of care device

The swab should then be inserted into the single-use elution buffer tube containing the elution buffer and stirred 5 times. The swab should then be safely discarded in clinical waste. A volume of 200ul of buffer is then transferred to the sample chamber of the device using the fixed volume pipette provided. The assay should be performed according to the 'Instructions For Use' provided with the device. The device is turned on, the reaction started and results reported by turning a dial positioned on the device. The device automatically heats the sample and re-suspends lyophilised reagents contained within the device, initiating isothermal amplification. Heating and mixing are provided by the device and the result reported on the lateral flow strip contained within the device. Results are indicated by the clear presence or absence of a black line displayed on the lateral flow strip which corresponds to a specific pathogen on the device label. Results require no calibration, interpretation, or calculation. The total time to result is expected to be approximately 10 minutes. The pathogens

which will be tested in the test device include one or more of the following: influenza A, influenza B, respiratory syncytial virus, human rhinovirus/enterovirus, human metapneumovirus, parainfluenza viruses (1-4).

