5.52 Data Collection

Medical and demographic data will be collected during the study and documented on the following case report forms (CRFs).

- Baseline CRF – Including demographic information, medical history, symptoms, signs and observations at the time of recruitment
- Results CRF – Including results from the POC device, how many devices were required to obtain a results, any issues with the device, results of the standard viral PCR results, patient outcomes and use of anti-viral treatment.

Additional data will be collected where required using the following CRFs:

- Adverse Events/Serious Adverse Events CRF – refer to section 7 for details
- Withdrawal CRF – to be completed if patient withdraws consent.

This data will be collected by a clinical research fellow or research nurses using participant hospital records or from the participant directly. In addition, pseudo-anonymised test results and imaging reports maybe collected. This could include but will not be limited to X-ray reports, CT scan reports, and pathology reports.

Physical copies of personal data will be kept in a secure records room in ICRRU. This records room has a combination lock code only known to the clinical research team. This records room is further contained in a secure area of the ICRRU which requires swipe-card access.

Personal data will be kept in pseudo-anonymised form. Each participant will be given a study number with a link code which can be used to refer to the participant's information. This link code will only be available to the clinical research team on a NHS computer. Data arising from the study, for publication or dissemination will retain no link to the original participant, and participants will not be identifiable from any published or disseminated materials. Anonymised (removing the link code and removing any link to original participant data), non-identifiable, information may be shared with academic collaborators.

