7.2 Statistical analysis

Only suitably qualified members of the clinical research team will have access to the personal data of the study participants. Anonymised, non-identifiable, information may be shared with academic collaborators. Clinical data will be extracted from the patient or from an electronic health record system (eg Cerner). This will be recorded in a paper or an electronic case report form (CRF). On this CRF there will be an audit trail of the staff entering the data. The CRF will be transcribed to a database. Statistical analysis software will also be used to calculate sensitivity, specificity, positive predictive values and negative predictive values.

8. Regulatory Issues

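### Does the plan need a written rule for how failed or repeated devices enter the accuracy figures?

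*Combined protocol and SAP*

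**What the plan says.** Section 3 (Study Design) states the fresh-testing minimum as "A minimum of 50 devices will be tested with fresh patient samples in a real life clinical setting". The same section states recruitment in patients: "A target of 200 patients has been set based on 1600 viral PCRs taken at ICHNT last year over the influenza period". Each recruited patient gives one study swab, which is either tested promptly or stored if no device is to hand.

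Section 3 makes feasibility and diagnostic accuracy on fresh samples the primary outcome, with accuracy assessed "using sensitivity, specificity, positive predictive value and negative predictive values". Section 2.1 adds: "Usability, performance and final results from the new POC device will be analysed in an acute clinical setting".

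Section 5.3 describes the read-out: "Results are indicated by the clear presence or absence of a black line displayed on the lateral flow strip". For running the assay it defers to the manufacturer's instructions, which are not among the documents. Section 5.52 lists what the Results CRF holds, including the device result and "how many devices were required to obtain a results, any issues with the device".

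On the calculation itself, Section 7.2 says only: "Statistical analysis software will also be used to calculate sensitivity, specificity, positive predictive values and negative predictive values".

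**The concern.** The minimum is counted in devices and recruitment in patients. The CRF shows that the study team expects some results to take more than one device. The statistical section does not say whether the unit is the device or the patient, which device result counts when there are several, or where a patient with no result goes.

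At least two approaches are defensible. One takes the final valid result for each patient, which describes the assay when it works. The other takes the first device and counts a failure as not detected, which describes what a single-use product delivers at first attempt. They can give different sensitivities from the same data, and more patients would not close the gap. If the choice were made after the results were known, it could follow them. The share of patients with a result from the first device also bears on feasibility, yet it is not a named measure.

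**Working it through.** **Stated figures.** The 50 devices and 200 patients come with no precision, power, prevalence or failure-rate input. Section 3 gives practical grounds for the 200. There is no calculation to reproduce.

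**Step 1: what the text implies about the unit.**
- Section 3: one study swab per patient, compared with that patient's routine sample(s). The natural pair is one device result and one reference result per patient.
- Section 5.52: the CRF counts the devices needed to reach a result. Several devices are steps towards one result, not several results.
- Section 2.1: final results are to be analysed.

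Together these point to one final result per patient. A device-level two-by-two table is a weak reading.

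**Step 2: whether a failed run can be told from a negative.** Section 5.3 describes only a line present or absent. The CRF field in Section 5.52, however, makes sense only if a device that gives no result is recognised as such, and device issues are recorded beside it. The operational definition may be in the manufacturer's instructions, which cannot be checked here.

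**Step 3: how far the two rules differ.** Let s be sensitivity among valid runs and f the share of first devices that fail. Assume that failure is unrelated to infection, that every failed run is successfully repeated, and that repeats have the same sensitivity. Then:
- final valid result: s
- first device, failure counted as not detected: s(1−f)
- difference: s·f

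The value of s is taken from the 90–99% background range for nucleic acid tests in Section 1.1. It is not a design assumption. The values of f are assumed.

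| s | f = 5% | f = 10% | f = 20% |
|---|---|---|---|
| 90% | 85.5% (drop 4.5) | 81.0% (9.0) | 72.0% (18.0) |
| 99% | 94.05% (4.95) | 89.1% (9.9) | 79.2% (19.8) |

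At f = 1% the drop is 0.90 × 0.01 to 0.99 × 0.01, about 1 point. Specificity moves little: if failures are read as negative, 95% becomes 0.95(1−f) + f, which is 95.25% at f = 5% and 96.0% at f = 20%.

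**Step 4: a small example.** Assume 50 patients and 40% prevalence, so 20 positives. Two of the 20 first devices fail, and 17 of the 18 valid first runs detect the virus.
- First device, failures as not detected: 17/20 = 85.0% (exact 95% CI 62.1–96.8%).
- Final valid result, both repeats successful: 17/20 to 19/20, that is 85.0% to 95.0% (for 19/20, CI 75.1–99.9%).
- The two patients excluded altogether: 17/18 = 94.4% (CI 72.7–99.9%).

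Exclusion is a third rule. It coincides with the final-result rule only when no repeat gives a result. At this size the intervals overlap widely.

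**Step 5: devices and patients.** If runs are repeated until a result is obtained, 50 devices yield on average 50(1−f) patients: 47.5, 45 and 40 at f = 5%, 10% and 20%. Section 3 calls 50 a minimum and aims to recruit as many patients as possible, so this affects how the count is described rather than whether the analysis is valid.

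**Step 6: whether anything is lost.** The CRF count and issues entry show which patients needed more than one device. The first-device success rate, the first-device table and the final-result table can all be built from data already collected.

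**The case for a change.** The strongest case for a change is that the omission is certain and cheap to repair. A phrase about final results does not say what happens to a patient who never gets one. Instructions for running a test would not normally fix a study's denominator. The hypothesis is about feasibility, so first-attempt success is close to the main question, and choosing a rule after seeing the data invites the flattering one.

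Part of this stands. Section 7.2 is silent on patients without a result, and a careful report would list them and give the first-device success rate. Section 3 also leaves open whether the 50 may include repeats.

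The rest carries less weight. The plan's wording already favours one rule, so the analyst does not choose between equals. Under Section 3 the operator is blinded to the standard-of-care result, so a decision to repeat a run should not be steered by the reference. Results are not disclosed and do not affect care. Because failures and repeats are recorded, both tables can be shown side by side, which removes most of the room for selective choice.

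**Conclusion.** No change to the plan is needed. Sections 2.1, 3 and 5.52, read together, give a sound accuracy table with one final result per patient and with failures and repeats on record. What is unwritten is how first-device failures and patients without a result are presented. Analysts can settle that from the existing CRF fields, with no new data.

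The numerical effect rests wholly on an assumed failure rate. With 5–20% first-device failures unrelated to infection, and 90–99% sensitivity among valid runs, the two rules differ by 4.5 to 19.8 points. The upper end needs both maxima, and at 1% failures the difference is about 1 point. In a feasibility study meant to help develop a prototype, this is a reporting detail. The conclusion assumes that the CRF is completed as Section 5.52 describes and that the manufacturer's instructions let operators recognise a failed run. The documents do not allow the second assumption to be checked.

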5.4 Banking samples

If no test device is available, the swab should then be inserted into a Copan UTM MINI 1ML, snapped off at the breakpoint and the tube capped. The sample should then be stored in the fridge at 4°C, or frozen at -20°C if freeze-thaw can be avoided, before transfer to long-term storage at -80°C in the lab as soon as possible and within 24 hours.

Samples that are not used immediately will be stored on-site at Imperial College Healthcare NHS Trust for the duration of the trial and transferred to Sense Biodetection Ltd ([name]) once the trial concludes. Researchers associated with the trial will have access to the samples and associated anonymised data. These may also be used in other ethically approved research studies by Imperial College London or our collaborators in the UK and abroad. The samples and the research results will be completely anonymised and there is no way that you can be identified through the stored samples.

Storage by research team of biological material which is not “relevant material” for the purposes of the Human Tissue Act.

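### The fresh-versus-stored comparison includes PPV and NPV with no pairing or common prevalence described, so these two measures could differ even if the device is equally accurate in both sets

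*Combined protocol and SAP*

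**What the plan says.** Section 2.2 (Secondary aims and objectives) says that sensitivity, specificity, PPV and NPV "in fresh samples will be calculated and compared to the results on stored samples". Section 3 (Study Design) makes this the secondary outcome: fresh samples in the clinic "compared to the laboratory settings using stored samples using sensitivity, specificity, positive predictive values and negative predictive values". All four measures are therefore comparison measures.

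Stored samples are not defined. Section 2.2 also mentions analytical study data, which this document does not describe.

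The handling of study samples is clearer:

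- Section 3: "One nasal swab to be taken per patient recruited", on top of the standard-care swab(s).
- Section 3: that swab is tested promptly or, "if no device is available for prompt testing, add the swab to a viral storage/transport buffer tube", frozen for later testing.
- Section 5.3: after elution for a prompt test the swab is thrown away. No retained aliquot is described.
- Section 5.4: "Samples that are not used immediately will be stored on-site at Imperial College Healthcare NHS Trust for the duration of the trial", after which they go to the device company.

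On analysis, Section 7.2 offers only this: "Statistical analysis software will also be used to calculate sensitivity, specificity, positive predictive values and negative predictive values". It mentions no confidence interval, pairing or handling of prevalence.

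**The concern.** PPV and NPV describe a test in a particular population. They combine the device's accuracy with the proportion of samples that are truly positive. Comparing them between two sample sets isolates the device only if prevalence is the same in both, or is made the same in the analysis.

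Nothing described here ensures that. If the stored samples are the study bank, a swab is either tested fresh or banked. The sets are then different patients, allocated by device availability and not at random. Recruitment is planned from 1/11/19 to 30/4/20, and prevalence could change over that window. If the stored samples come from another source, the plan describes neither pairing nor a prevalence match. If fresh and stored results came from the same patients, prevalence would be equal and the point would fall away, but no such arrangement is described.

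At stake is the reading of a secondary result. A PPV or NPV gap could be reported as the device doing better or worse at the bedside than in the laboratory when only the mix of positives and negatives differs.

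**Working it through.** **No planned figure to reproduce.** The plan gives no number for this comparison. The target of 200 patients is pragmatic (200/1600 = 12.5% of the previous season's viral PCRs), and no prevalence is stated.

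**Inputs.** Sensitivity (Se) 90–99% and specificity (Sp) 95–99% are the Section 1.1 table's figures for second-generation NAAT tests. They are illustrative and not a claim about this device. Every prevalence p below is an assumption. Se and Sp are held identical in the two sets and only p changes.

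**Formulas.**

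- PPV = Se·p / [Se·p + (1−Sp)(1−p)]
- NPV = Sp(1−p) / [Sp(1−p) + (1−Se)p]

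**Mid-range case, Se 95%, Sp 97%, prevalence 20% v 30%.**

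- PPV: 0.190/0.214 = 88.79% v 0.285/0.306 = 93.14%, a gap of 4.35 points.
- NPV: 0.776/0.786 = 98.73% v 0.679/0.694 = 97.84%, a gap of 0.89 points.

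**Corners of the range, 20% v 30%.**

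| Se / Sp | PPV | PPV gap | NPV | NPV gap |
|---|---|---|---|---|
| 90 / 95 | 81.82 v 88.52 | 6.71 | 97.44 v 95.68 | 1.75 |
| 90 / 99 | 95.74 v 97.47 | 1.73 | 97.54 v 95.85 | 1.69 |
| 99 / 95 | 83.19 v 89.46 | 6.26 | 99.74 v 99.55 | 0.19 |
| 99 / 99 | 96.12 v 97.70 | 1.58 | 99.75 v 99.57 | 0.18 |

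**Other assumed prevalences.** At 10% v 30% the corner gaps are 6.0 to 21.9 points for PPV and 0.3 to 3.2 for NPV. At higher prevalence the order can reverse. With Se 95%, Sp 97% and 40% v 60%:

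- PPV: 0.380/0.398 v 0.570/0.582, a gap of 2.5 points.
- NPV: 0.582/0.602 v 0.388/0.418, a gap of 3.9 points.

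Section 5.3 allows one or more of several pathogens on the device. The relevant prevalence could therefore be low (one uncommon virus) or high (any virus).

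**Sampling error, for scale.** Assume 50 fresh samples (the Section 3 minimum) and 150 stored (200 − 50), with Se 95% and Sp 97%. Hold the positives at exactly 10/50 and 30/150, so prevalence is 20% in both. In simulation the central 95% of fresh-minus-stored PPV differences runs from −19.7 to +18.2 points. If the positives also vary by chance around a true 20%, it runs from −25.0 to +19.4. These ranges are noise, not bias.

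**What standardising does.** Take invented counts with identical accuracy (Se 90%, Sp 95%):

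- Fresh: 9/10 positives and 38/40 negatives correct. PPV 9/11 = 81.8%, NPV 38/39 = 97.4%.
- Stored: 45/50 positives and 95/100 negatives correct. PPV 45/50 = 90.0%, NPV 95/100 = 95.0%.

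Prevalence is 20% v 33%. At a common 20%, both sets give PPV 0.18/0.22 = 81.8% and NPV 0.76/0.78 = 97.4%, so the apparent gap disappears.

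**The case against.** **No prevalence difference is shown.** This stands. On the study-bank reading both sets share eligibility criteria, Trust and season. Allocation by device availability is non-random, but that does not show a different prevalence. A reader might infer that the comparison is bound to be biased; the documents support only that it could be.

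**Sampling error is the bigger problem.** This also stands. The 4.35-point shift lies well inside the simulated range. A reader might count chance variation in prevalence as part of the bias. It is not: an interval for the observed values would reflect it. A true prevalence difference is another matter, because it would persist in larger samples.

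**NPV hardly matters.** A reader might conclude this from the 20% v 30% figures. The 40% v 60% case contradicts it, and without a stated prevalence there is no basis for setting NPV aside.

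**The stored samples may be described elsewhere.** This is possible, given the reference to analytical study data. A reader might take the comparison as certainly unpaired, but that follows only if the stored samples are the study bank. The samples should be identified before the method is fixed.

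**Sensitivity and specificity are already listed, and nothing says a PPV gap will be attributed to the device.** Both are true, and they keep the point small. They do not remove it, because PPV and NPV are named as comparison measures in two sections with no caution attached.

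**Conclusion.** The point holds as a minor one. As written, the secondary outcome compares two prevalence-dependent measures between sets that are unpaired on the study-bank reading, or of undescribed relation otherwise. With identical device accuracy, an assumed 20% v 30% prevalence moves PPV by 1.6 to 6.7 points and NPV by 0.2 to 1.8 across the protocol's NAAT range. Other assumed prevalences give larger PPV shifts or reverse which measure moves more.

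The size rests wholly on assumed prevalences. The mechanism does not. Sensitivity and specificity avoid the direct dependence on prevalence, but they can still differ through case mix and storage. The consequence is a possibly misleading statement in a descriptive secondary outcome with no test or decision rule. The primary outcome and patient care are unaffected.

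**What to change.** In Sections 2.2 and 3:

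1. State which samples are the stored samples, and whether any come from the same patients as the fresh ones.
2. Base the fresh-versus-stored comparison on differences in sensitivity and specificity with 95% confidence intervals. Use unpaired score or exact methods if the patients differ, and paired methods if they are the same.
3. Report PPV and NPV for fresh samples only, or for both sets at one stated prevalence. Give 2×2 counts and observed prevalence by set.
4. Say that unstandardised PPV or NPV gaps will not be read as differences in device performance, and that differences in sensitivity or specificity may reflect case mix or storage.

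The cost is a few sentences. On the study-bank reading no new patients or swabs are needed, because the Results CRF (Section 5.52) already records the device result and the "results of the standard viral PCR results". This depends on later device results from banked samples staying linked to that reference result. Section 5.4 describes the samples as fully anonymised and moving to the company after the trial, so the link should be stated. If the stored samples come from elsewhere, the CRF does not cover them and the cost cannot be judged from these documents.

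The conclusion will also be more cautious. For an assumed 9/10 v 27/30, the score interval for the difference in sensitivity is −31 to +18 points. That imprecision is already in the design, and this change would only make it visible.
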